6.2.2. Exclusion Criteria

Patients meeting any of the following criteria will not be included in the study:

- Received advanced treatment prior to the study index date.
- Prescription records with negative days of supply will be excluded from all the analyses except in cost variable calculation. The day of supply for claims with missing or 0 days will be imputed.
- Only one RCC diagnosis in the 12 months prior or one month post index date.
- Patients with data for analysis (<3 months post index date).

PFIZER CONFIDENTIAL

[REDACTED]

6.3. Variables

6.3.1. Treatment Pattern Variables

Table 5. Treatment Pattern Variables

Variable	Operational definition
Initial (1L)Treatment Regimen	The first treatment regimen prescribed following a primary and secondary diagnosis of advanced/metastatic disease.
Monotherapy vs Combo therapy	Categorical: Yes/No Combo therapy is defined by a second medication filled on or within 30 days of the original medication and the original medication is filled subsequently. CCI [REDACTED]
Time to FL treatment received	Continuous: days Length of time (days) from the first mRCC diagnosis (first ever secondary malignancy code associated with RCC) to first line therapy prescription.
Treatment discontinuation date (by LoT) – to be used for time to treatment failure (TTF) and time to next line of therapy	Date Treatment discontinuation indicating the end of LOT will be identified as the earliest of: 
For oral therapy: to the run-out date of the last prescription (ie, date of last prescription plus days supply) in the same treatment line.For non-oral therapy: 30 days after the last observed prescription/administration prior to at least a 30 day gap in therapy of all agents included in the first line of therapy.1 day before a new prescription/administration date, whichever occurred earlier.For multiple drug regimens: the above would be triggered by the last prescription/administration in the regimen.Death.End of enrollment.
Days of continuous treatment (by LoT)	Continuous: days The duration of each LOT will be measured from the first prescription or administration of line of therapy medication(s) to the end of the line of therapy, allowing for 30 day allowable gaps in therapy.
Treatment Continuation	Categorical (Y/N) There is no >30 day gap (ie, persistent treatment) for the index medication during follow-up period.

PFIZER CONFIDENTIAL

[REDACTED]

Variable	Operational definition
Treatment Interruption	Categorical (Y/N) At least one instance of >30 day gap (ie, non-persistent treatment) for the index medication during follow-up period or LOT followed by resuming therapy (not mutually exclusive with switch, augment, discontinuation, but a sub-group within LOT).
Interrupted treatment duration	Continuous: days Time from index medication to treatment discontinuation for those within treatment interruptions (>30 day gaps). Represents the time between index and end of last treatment, including any treatment gaps.
Regimen change (switching)	Categorical: Yes/No At least one non-index advanced/metastatic RCC medication during or after the period of the last persistent index medication prescription's days supply plus the 30 day gap (and before re-initiation of index medication or follow-up, if after).
Regimen change (augmentation)	Categorical: Yes/No Addition of treatment to initial therapy prescribed, ie, initiation of a new therapy different from the initial therapy while continuation of the initial therapy.
Line of therapy definitions	Categorical: 1L vs. 2L vs. >=3L.
Treatment sequence	Categorical: Based on observed treatment sequences. Treatment Sequence – Sequence of successive therapies for mRCC from 1L to 2L to 3L (stop after 3L).
Patient's status at end of follow-up	Categorical: end of enrollment, end of data availability, death. Patient is in one of the following mutually exclusive categories at the end of follow-up.

PFIZER CONFIDENTIAL

[figure not shown]

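### Table 5 gives non-oral lines a 30-day gap rule and oral lines none, so on a literal reading time to treatment failure depends on route of administration

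*Combined protocol and SAP*

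**What the plan says.** Section 6.3.1, Table 5, has a row for the treatment discontinuation date by line of therapy (LOT). Its label says the date is "to be used for time to treatment failure (TTF) and time to next line of therapy". The row opens: "Treatment discontinuation indicating the end of LOT will be identified as the earliest of" a list of dates, and the list differs by route:

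- Oral therapy: "to the run-out date of the last prescription (ie, date of last prescription plus days supply) in the same treatment line". No gap is mentioned.
- Non-oral therapy: "30 days after the last observed prescription/administration prior to at least a 30 day gap in therapy of all agents" in the first line.
- Multi-drug regimens: "the above would be triggered by the last prescription/administration in the regimen".
- The remaining dates are the day before a new prescription or administration, death, and end of enrollment.

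Two other rows of Table 5 bear on the same question and are not split by route. Days of continuous treatment is measured "to the end of the line of therapy, allowing for 30 day allowable gaps in therapy". Treatment Interruption, meaning a gap of more than 30 days followed by resumption, is described as "not mutually exclusive with switch, augment, discontinuation, but a sub-group within LOT".

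Section 6.7 says that no separate SAP is required, and Section 6.8 says that analyses are programmed to the protocol's specifications. The wording of Table 5 is therefore what a programmer will code.

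**The concern.** The two route-specific rules answer different questions. The non-oral rule looks for a stop followed by a gap. The oral rule looks for the last fill in the line, and if a restarted drug stays in its line, that fill comes after the gap. A patient who stops, restarts and stops again would then be dated at the second stop on an oral drug and at the first on an injectable.

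TKI monotherapy is oral, and IO monotherapy and IO+IO are injectable. All three are first-line cohorts in Section 5. Section 6.7 plans Kaplan-Meier curves for duration of therapy, and Analysis 3 in Section 6.1 uses TTF to show unmet need with current regimens, giving ipilimumab/nivolumab as the example. A rule that shortens TTF only for injectables would push those displays in one direction. Replication across the databases (Section 6.4) would reproduce the artefact, not expose it.

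**Working it through.** The plan gives no interruption rate, sample size or TTF estimate, so there is no planned figure to reproduce. The check sets the relevant text side by side and then applies both rules to identical dates.

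**1. What the text implies about a gap of more than 30 days**

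| Text | Split by route? | Implication |
|---|---|---|
| Table 5, discontinuation date, oral | yes | no gap condition |
| Table 5, discontinuation date, non-oral | yes | line ends at the gap (all agents) |
| Table 5, days of continuous treatment | no | suggests a line ends at the gap, but measures to an end of line that the row above defines |
| Table 7 and Section 6.1, percent discontinuing | no | discontinuation is a gap over 30 days without a new treatment |
| Table 5, switching | no | applies the 30-day gap to days supply |
| Table 5, interruption | no | a line can contain such a gap |
| Section 6.1, treated period | no gap rule for either route | runs to the last prescription |

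Table 7's discontinuation entry defines a percentage, not a date, and its TTF entry states no gap rule. Only the first two lines of the table belong to the row assigned to TTF. That the *first* gap counts is not written; it follows from taking the earliest date.

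**2. One interrupted patient (assumed dates)**

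Covered days 0 to 90, 60 days off, covered days 150 to 240. The injectable interval is 28 days, as Table 9 imputes for nivolumab.

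- Oral end = 150 + 90 = day 240.
- Injectable: last dose before the gap = 90 − 28 = day 62; end = 62 + 30 = day 92.
- Difference with full follow-up = 240 − 92 = 148 days.
- Section 6.1 sets the main outcomes period at 6 months (about day 183). Truncated there, the difference = 183 − 92 = 91 days.

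**3. Effect on mean TTF (assumed 10% to 30% of patients with this pattern)**

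- Full follow-up: 0.10 × 148 = 14.8 to 0.30 × 148 = 44.4 days.
- Truncated at 6 months: 0.10 × 91 = 9.1 to 0.30 × 91 = 27.3 days.

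**4. A second schedule, on a strict 28-day grid**

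Day 62 in step 2 is not a multiple of 28, so the rules were also applied to 28-day supplies starting on days 0, 28, 56, then 130, 158, 186. The gap is 130 − (56 + 28) = 46 days.

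- As written: oral 186 + 28 = 214; non-oral 56 + 30 = 86; difference 128 days.
- Both routes end at the gap: 84 against 86.
- Both routes run through the gap: 214 against 216.

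Either common rule brings the routes within 2 days. The remainder is 30 days credited after an injection against a 28-day supply.

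**5. Simulation with identical behaviour on both routes**

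Assumptions, none from the documents: 20,000 patients per scenario, 28-day cycles, exponential time on treatment with median 240 days, each interruption adding 45 days, no truncation.

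| Chance of interruption per cycle | Patients interrupted | Median TTF, oral as written | Median TTF, non-oral as written | Median TTF, oral with the gap rule |
|---|---|---|---|---|
| 0 | 0% | 252 | 254 | 252 |
| 1% | 11% | 252 | 226 | 224 |
| 2% | 19% | 252 | 198 | 196 |
| 5% | 38% | 280 | 170 | 168 |
| 10% | 55% | 286 | 114 | 112 |

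With 11% and 19% interrupted, the medians differ by 26 and 54 days from the rule alone.

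**The case against.** The strongest reply is that the oral rule should not be read in isolation. The allowable-gap row, the discontinuation definition in Table 7 and Section 6.1, and the switching row all apply 30 days without regard to route, and on those an oral line also ends at the gap. The interruption row is equally route-neutral: if it keeps a restarted TKI in its line, it keeps a restarted IO drug in its line too, and the treated period in Section 6.1 runs to the last prescription on both routes. This stands. A reader might infer that the plan definitely favours TKIs; the documents do not go that far, because they never state one gap-and-restart rule.

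A reader might also extend the point to every IO regimen. That fails for IO+TKI: the non-oral rule needs a gap in all agents and the multi-drug rule looks to the last fill or administration, so continued TKI fills keep the line open across an IO gap. The contrast is cleanest for IO monotherapy, which is a Section 5 cohort but is not named in the regimen focus list of Section 6.1.

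Finally, the analysis is descriptive, Section 6.9 disclaims causal inference, and interruption and interrupted duration are reported separately. That lowers the severity. It does not remove the problem, because the TTF and duration displays would still rest on the disputed date.

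**Conclusion.** The point holds as an unresolved inconsistency with a route-dependent result on the literal reading. Coded as written, with the interruption row, the row that defines TTF runs through interruptions for TKI monotherapy and stops at them for IO monotherapy and IO+IO. TKI TTF would then look longer for the same treatment behaviour. The conflicting passages do not cure this, since none of them is the row assigned to TTF.

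The size is unknown, because it depends on an interruption rate and a gap pattern that the documents do not give. The 148-day figure needs follow-up beyond the 6-month main outcomes period; for that period, about 91 days per interrupted patient and about 9 to 27 days in the mean is the relevant illustration. With no interruptions the routes differ by only 2 days in the simulation. As the study is descriptive, this should be fixed, but it does not undermine the study as a whole.

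**What to change.** Use one gap rule for both routes in the Table 5 discontinuation-date row. The simplest way is to give the oral rule the same condition: the line ends at the run-out of the last fill before the first gap of more than 30 days in all agents of the regimen, or at the run-out of the last fill if there is no such gap. Use that date for TTF and for days of continuous treatment.

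That change alone would leave other text in conflict, so also:

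- State that resuming the same drug after such a gap does not start a new line and is counted only under Treatment Interruption and Interrupted treatment duration, and reword the interruption row to match.
- Align Table 7 and the treated-period definition in Section 6.1 with the chosen rule.
- Choose between a gap of at least 30 days and one of more than 30 days; the non-oral rule uses the former and the other definitions the latter.
- Say how the rule applies to IO+TKI, where one agent may continue through a gap in the other.

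Running through gaps on both routes would also remove the route dependence; the recommended version fits the 30-day allowance elsewhere, and time through gaps already has its own row. The cost is edits to a few definitions and one programming rule. TKI durations become somewhat shorter than the current literal wording gives.

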6.3.2. Baseline Variables

Table 6. Baseline Variables

[figure not shown]
Variable	Operational definition
Baseline demographics	
Index Date	Date of first RCC diagnosis on record
Index Year	Index year for the patient
Age	Continuous: Years Patient age at index date
Sex	Categorical: Male or female
Insurance Coverage	Categorical: Commercial, Medicare, or Medicaid
US Region	Categorical: Northeast, Midwest, South, West
Race	Categorical: based on each database
Clinical characteristics	
Time to systemic therapy <1 year	From IMDC: <1 year from time of diagnosis to systemic therapy
NCI Charlson comorbidity index (DCI)	Categorical: 0, 1-2, 3+
History of smoking	Categorical: Yes/No Prior history of smoking – record of smoking cessation medication or V code.
History of systemic therapy	Categorical: Yes/No A record of being given certain systemic drugs (interferon, interleukin 2, gemcitabine and doxorubicin)
History of surgical resection	Categorical: Yes/No History of nephron sparing or radical nephrectomy. ICD-10-CM Z90.5/ICD-9-CM V45.73 Acquired absence of kidney.

PFIZER CONFIDENTIAL

Variable	Operational definition
History of radiation therapy	
Categorical: Yes/No
 
ICD-10-CM Z51.0/ICD-9-CM V58.0 Encounter for radiotherapy.
 
ICD-10-PCS › D › Urinary System:
 
• DT0 Beam Radiation;• DT1 Brachytherapy;• DT2 Stereotactic Radiosurgery;• DTY Other Radiation. 
CPT Codes:
 
77401 Radiation treatment delivery, superficial and/or ortho voltage, per day;
 
77402 Radiation treatment delivery, >1MeV; simple;
 
77407 intermediate;
 
77412 complex.
 
New Codes
 
77085 Dual-energy x-ray absorptiometry (DXA), bone density study, 1 or more sites; axial skeleton (eg, hips, pelvis, spine), including vertebral fracture assessment.
 
77086 Vertebral fracture assessment via dual energy X-ray absorptiometry (DXA).
 
77306 Teletherapy isodose plan; simple (1 or 2 unmodified ports directed to a single area of interest), includes basic dosimetry calculation(s).

PFIZER CONFIDENTIAL

[figure not shown]

Variable	Operational definition
	
77307 complex (multiple treatment areas, tangential ports, the use of wedges, blocking, rotational beam, or special beam considerations), includes basic dosimetry calculation(s).
 
77316 Brachytherapy isodose plan; simple (calculation[s] made from 1 to 4 sources, or remote afterloading brachytherapy, 1 channel), includes basic dosimetry calculation(s).
 
77317 intermediate (calculation[s] made from 5 to 10 sources, or remote afterloading brachytherapy, 2-12 channels), includes basic dosimetry calculation(s).
 
77318 Intensity modulated radiation treatment delivery (IMRT), includes guidance and tracking, when performed; simple.
 
77385 Intensity modulated radiation treatment delivery (IMRT), includes guidance and tracking, when performed; simple.
 
77386 complex.
 
77387 Guidance for localization of target volume for delivery of radiation treatment delivery, includes intrafraction tracking, when performed.
 
Deleted Codes (may be in the historic data, though no longer in use)
 
72291 Radiological supervision and interpretation, percutaneous vertebroplasty, vertebral augmentation, or sacral augmentation (sacroplasty), including cavity creation, per vertebral body or sacrum; under fluoroscopic guidance.
 
72292 under CT guidance.
 
74291 Cholecystography, oral contrast; additional or repeat examination or multiple day examination.
 
76645 Ultrasound, breast(s) (unilateral or bilateral), real time with image documentation.
 
76950 Ultrasonic guidance for placement of radiation therapy fields.
 
77080 Dual-energy X-ray absorptiometry (DXA), bone density study, 1 or more sites; axial skeleton (eg, hips, pelvis, spine).
 
77305 Teletherapy, isodose plan (whether hand or computer calculated); simple (1 or 2 parallel opposed unmodified ports directed to a single area of interest).
 
77310 intermediate (3 or more treatment ports directed to a single area of interest).

PFIZER CONFIDENTIAL

Variable	Operational definition
	
77315 complex (mantle or inverted Y, tangential ports, the use of wedges, compensators, complex blocking, rotational beam, or special beam considerations).
 
77326 Brachytherapy isodose plan; simple (calculation made from single plane, 1 to 4 sources/ribbon application, remote afterloading brachytherapy, 1 to 8 sources).
 
77327 intermediate (multiplane dosage calculations, application involving 5 to 10 sources/ribbons, remote afterloading brachytherapy, 9 to 12 sources).
 
77328 complex (multiplane isodose plan, volume implant calculations, over 10 sources/ribbons used, special spatial reconstruction, remote afterloading brachytherapy, over 12 sources).
 
77403 Radiation treatment delivery, single treatment area, single port or parallel opposed ports, simple blocks or no blocks; 6-10 MeV.
 
77404 11-19 MeV.
 
77406 20 MeV or greater.
 
77408 Radiation treatment delivery, 2 separate treatment areas, 3 or more ports on a single treatment area, use of multiple blocks; 6-10 MeV.
 
77409 11-19 MeV.
 
77411 20 MeV or greater.
 
77413 Radiation treatment delivery, 3 or more separate treatment areas, custom blocking, tangential ports, wedges, rotational beam, compensators, electron beam; 6-10 MeV.
 
77414 11-19 MeV.
 
77416 20 MeV or greater.
 
77418 Intensity modulated treatment delivery, single or multiple fields/arcs, via narrow spatially and temporally modulated beams, binary, dynamic MLC, per treatment session.
 
77421 Stereoscopic X-ray guidance for localization of target volume for the delivery of radiation therapy.

PFIZER CONFIDENTIAL

Variable	Operational definition
Location of metastasis	
Categorical: by location (% of patients for each):
 

 Lymph nodes (ICD9-196.xx, ICD10 – C77)
 Lung (ICD9-197.0x, ICD10-C78.00)
 Liver (ICD9-197.7x, ICD10-C78.7)
 Brain (ICD9-198.3x, ICD10-C79.31)
 Bones (ICD9-198.5x, ICD10-79.5x)
 Adrenal gland (ICD9-198.7x, ICD10-79.7)
 Other (ICD9 196.xx-199.xx and ICD10 C77-C80 exclusive of above categories)
Severe renal impairment	
Categorical: Yes/No
 
ICD-9: 588.89, 588.9, 593.9, 274.02, 274.03
 
ICD-10: M10.3x, M1A.3x, N25.89, N25.9

Moderate-to-severe hepatic impairment	
Categorical: Yes/No
 
ICD-9: 571, 572, 573
 
ICD-10: K70.4x, K71.0, K71.1X, K72, K73, K75, K76, K77

Constipation	
Categorical: Yes/No
 

• ICD9 code: 564.0x; ICD10 code: K59.0
Nausea	
Categorical: Yes/No
 
ICD9 code: 787.01; ICD10 code: R11.0, R11.2

PFIZER CONFIDENTIAL

[figure not shown]

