Treated Period Follow-Up. Patients will be followed over the period treated with advanced RCC therapy. Time treated will be defined as the time from the index date to the date of the end of the last advanced metastatic RCC prescription (end of supply for orals/administration date plus 30 days for injectables), end of enrollment, end of follow up, or death (see more specifics on oral versus injectable rules in [6.3.1 Variables](#) section of this protocol).

Analysis 2. Describe various treated populations of interest by demographics, clinical characteristics, as well as cost and utilization

Describe the demographics and other baseline characteristics of the first-line treated cohorts of interest identified in the treatment patterns analysis (Analysis 1) for RCC patient as follows:

Baseline Characteristics (see [6.3.2 Baseline Characteristics](#)):

- Age at index;
- Gender;
- Race;
- Region;

PFIZER CONFIDENTIAL

- Payor;
- Clinical characteristics: Quan-Charlson Comorbidity Index (CCI) scores and baseline comorbidities;
- Prior treatment (6 months prior) - nephrectomy, radiation/ablation, interferon, high-dose interleukin-2, other anti-neoplastic medications;
- Secondary malignancy locations (6 months prior);
- Baseline costs of care (6 months prior);
- Baseline health care resource utilization (6 months prior).

Analysis 3: Evaluate the key outcomes of interest for advanced RCC therapy regimens toward demonstrating existing unmet needs in RCC given currently available therapies (eg, ipilimumab/nivolumab).

Treatment duration, discontinuation, interruption, switching and therapy augmentation will be presented, as will the burden of disease costs and health care utilization. Survival will also be explored, although regimens are too new for extensive follow-up time.

Overall Outcomes Study Period. For the outcomes analysis, follow-up will be defined as the time from the index date to the end of specified follow up period of 6 months, end of enrollment, or death. Follow-up may vary given sample sizes of study population, with by subanalysis using 1-year or 2-years of follow-up time from study index date for certain sub-populations.

Outcomes include:

- **Time to Treatment Failure (TTF)** – First line time to treatment failure (TTF) is defined as the time from first-line therapy start to treatment discontinuation for any reason, including switched, augmented therapy, end of enrollment, death.

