6.2.1. Inclusion Criteria

Subjects will be selected irrespective of their survival status. Patients must meet all of the following inclusion criteria to be eligible for inclusion in the study:

- **Index date:** The first prescription or administration of one of the medications indicated for advanced RCC recorded in the database between April 2018-March 31, 2019, among those with no aRCC treatment in their history.
- Age 18 years or older in the year of the index first line therapy prescription.
- 2 or more RCC diagnoses (ICD-9: 189.0; ICD-10: C64.1, C64.2, C64.9) at least 30 days apart, in the 1 year prior to the index date until 30 days post index date.

PFIZER CONFIDENTIAL

- 2 or more code for secondary malignancy codes indicating possible diagnoses for metastatic disease at least 30 days apart, in the 1 year prior to the index date until 30 days post index date. (ICD-9: xx-199.xx; ICD-10: C77-C79, except ICD9: 198.0 Secondary malignant neoplasm of the kidney and ICD10: C79.0 Secondary malignant neoplasm of the kidney and renal pelvis).
 - CCI [REDACTED]
- Continuous enrollment from 12 months prior to the index date. Patients will be required to have continuous enrollment from their index date until the end of the available data. This will allow for sub-analysis of cohorts with 3 months, 6 months and 12 months of available data.

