ANNEX 2. ADDITIONAL INFORMATION

Comorbidities	ICD-9-CM Codes	ICD-10-CM Codes
Quan CCI comorbidities (Quan 2005)		
AIDS	042.x–044.x	B20.x–B22.x, B24.x
Any malignancy	140.x–172.x, 174.x–195.8,	
200.x–208.x, 238.6	C00.x–C26.x, C30.x–C34.x, C37.x–	
C41.x, C43.x, C45.x–C58.x, C60.x–		
C76.x, C81.x–C85.x, C88.x,		
C90.x–C97.x		
Cerebrovascular disease	362.34, 430.x–438.x	G45.x, G46.x, H34.0, I60.x–I69.x
Chronic pulmonary disease	416.8, 416.9, 490.x–505.x,	
506.4, 508.1, 508.8	I27.8, I27.9, J40.x–J47.x, J60.x–J67.x,	
J68.4, J70.1, J70.3		
Congestive heart failure	398.91, 402.01, 402.11, 402.91,	
404.01, 404.03, 404.11,		
404.13, 404.91, 404.93,		
425.4–425.9, 428.x	I09.9, I11.0, I13.0, I13.2, I25.5, I42.0,	
I42.5–I42.9, I43.x, I50.x, P29.0		
Dementia	290.x, 294.1, 331.2	F00.x–F03.x, F05.1, G30.x, G31.1
Diabetes with complications	250.4–250.7	E10.2–E10.5, E10.7, E11.2–E11.5,
E11.7, E12.2–E12.5, E12.7, E13.2–		
E13.5, E13.7, E14.2–E14.5, E14.7		
Diabetes without chronic complications	250.0–250.3, 250.8, 250.9	E10.0, E10.1, E10.6, E10.8, E10.9,
E11.0, E11.1, E11.6, E11.8, E11.9,		
E12.0, E12.1, E12.6, E12.8, E12.9,		

PFIZER CONFIDENTIAL

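### The comorbidity index is named as Quan-Charlson in section 6.1 and Annex 2 but as NCI in Table 6, and the only code list counts the study cancer, which shifts the 0, 1-2, 3+ groups

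*Combined protocol and SAP*

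**What the plan says.** Section 6.7 says that no separate SAP is needed, so the protocol is the programming specification. The comorbidity score appears in three places:

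- Section 6.1, Analysis 2, lists among the baseline characteristics "Clinical characteristics: Quan-Charlson Comorbidity Index (CCI) scores and baseline comorbidities".
- Table 6 (section 6.3.2) has a row labelled "NCI Charlson comorbidity index (DCI", grouped as "Categorical: 0, 1-2, 3" (the last group is 3 or more). It gives no codes and no weights, and the abbreviation DCI is not in Table 1.
- Annex 2 gives a code list headed "Quan CCI comorbidities". Its row for any malignancy includes the ICD-9 ranges "140.x–172.x, 174.x–195.8". Its ICD-10 ranges include a block that starts at the end of "C41.x, C43.x, C45.x–C58.x, C60.x" and closes at the beginning of "C76.x, C81.x–C85.x, C88.x", that is, C60 to C76.

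Section 6.2.1 requires "2 or more RCC diagnoses (ICD-9: 189.0; ICD-10: C64.1, C64.2, C64.9", at least 30 days apart, between 1 year before and 30 days after index. It also requires two secondary-malignancy codes in the same window. Section 6.1 measures baseline characteristics over the 6 months before index. Index is the start of aRCC treatment in sections 6.1 and 6.2.1, but the first recorded RCC diagnosis in Table 6.

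**The concern.** There are two linked problems. First, the groups are attached to one index and the code list to another, so two programmers following the text could build different scores. The analysis is to be replicated in databases that may not be merged, so a difference in construction could be mistaken for a difference between populations.

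Second, the one available code list scores the disease that defines the cohort, and no visible text excludes it. With fixed cut-points, points added for the study cancer move patients between groups for a reason unrelated to their other illnesses. This is the only summary comorbidity score planned for describing the first-line cohorts, and section 6.7 calls for a standardized difference on every variable. The comparability of the IO and TKI cohorts on comorbidity would be read partly from it.

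**Working it through.** The plan gives no expected distribution for this variable, so there is no figure to reproduce. Three checks follow.

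**1. Are the entry codes inside the Annex 2 row?** ICD-9: 174 ≤ 189.0 ≤ 195.8, so yes. ICD-10: C60 ≤ C64 ≤ C76, so yes. The secondary-malignancy codes (ICD-9 196 to 199, ICD-10 C77 to C79) are not in that row. The annex as available stops within the diabetes rows, so whether a separate metastatic row exists cannot be seen, and its absence is not counted against the plan.

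**2. What happens to the groups?** Score = cancer weight + points from other comorbidities. The weight is an assumption because the documents give none.

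| Cancer weight | 0 other points | 1 other | 2 other | 3 other |
|---|---|---|---|---|
| 0 (study cancer excluded) | 0 | 1-2 | 1-2 | 3+ |
| 1 | 1-2 | 1-2 | 3+ | 3+ |
| 2 | 1-2 | 3+ | 3+ | 3+ |
| 3 or more | 3+ | 3+ | 3+ | 3+ |

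At any positive weight, no patient with a counted RCC code can be in group 0. At weight 1 the variable separates 0-1 from 2 or more other points. At weight 2 it separates none from any. Only at weight 3 or more does it stop separating patients.

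**3. Does entry force an RCC code into the 6-month baseline?** Number the days from -365 to +30. Pairs of days at least 30 apart: 366 × 367 / 2 = 67,161. Take the baseline as days -183 to -1. Pairs with neither day in it:

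- both in days -365 to -184 (182 days): 152 × 153 / 2 = 11,628
- one in that block and one in days 0 to 30: 182 × 31 = 5,642
- both in days 0 to 30: 1

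The total is 17,271, and 17,271 / 67,161 = 25.7%. This counts the date patterns that the rule allows; it is not an expected share of patients. It shows that group 0 is not empty by rule.

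For a rough share, assume that RCC claims arrive at random at r per month. The chance of none in 6 months is exp(-6r):

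| Claims per month (assumed) | No RCC claim in 6 months |
|---|---|
| 0.25 | 22% |
| 0.5 | 5.0% |
| 1 | 0.25% |
| 2 | 0.0006% |

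Group 0 is therefore nearly empty for regularly coded patients. Among patients with no other comorbidity, the few left in group 0 are there because of when RCC was billed.

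Under the Table 6 index date, the 6 months before the first recorded RCC code contain no RCC code by definition, and this problem would not arise. That date contradicts sections 6.1 and 6.2.1, so it is a further inconsistency and not a safeguard.

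**The case against.** The strongest reply is that the argument joins two things which the plan keeps apart: the groups belong to the NCI row, which has no code list, and the malignancy codes belong to the Quan list. Nothing in the documents shows that the NCI index counts malignancy. This stands, and it is why the conclusion about group 0 is conditional. It does not rescue the specification, because Annex 2 is the only list a programmer has.

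A second reply concerns the standardized difference. A reader might infer that counting the cancer understates imbalance between cohorts. The documents do not support that. Section 6.7 defines the measure as the absolute difference in means over a pooled standard deviation, and section 6.1 speaks of scores. If nearly all patients carry the same cancer weight, both quantities are unchanged for a continuous score. After grouping, the direction is open: at weight 1 the contrast between 2 and 3 other points is lost, but a contrast between 1 and 2 appears.

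Third, individual baseline comorbidities are also reported, with separate Table 6 rows for renal and hepatic impairment, and no adjusted model using the index is specified. This limits the consequence but does not repair the summary score.

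Finally, removing the whole malignancy row would discard other primary cancers, which are real comorbidity. This is accepted, and the fix is narrower.

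**Conclusion.** The naming conflict and the code overlap are plain on the page. If Annex 2 is applied to the Table 6 groups from treatment start, any patient with an RCC claim in the 6-month baseline cannot be in group 0, and the remaining groups are shifted to an extent that depends on an unstated weight. The size of group 0 rests on the assumed claim rates above.

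A reader might go further and conclude that everyone falls in 3+, or that the variable cannot describe comorbidity at all. That needs a cancer weight of 3 or more, which the documents do not state. At weights 1 and 2 the groups still reflect other illness, more coarsely and at different cut-points.

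The grouped variable is degraded, not useless. The effect is limited to the baseline table and grouped standardized differences of a descriptive study; no test or sample size is involved. The text is wrong as written and should be corrected before programming.

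**What to change.** - Name one index, with its codes and weights, and use the same name in section 6.1, Table 6 and Annex 2. Define or remove DCI.
- State that the RCC codes (ICD-9 189.0, ICD-10 C64.x) and the secondary-malignancy codes required for entry are left out of the score before 0, 1-2 and 3+ are formed. Keep other primary cancers.
- State that the score is computed over the 6 months before the treatment-start index date, and correct the conflicting index date in Table 6.

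With the study cancer excluded, a patient with no other comorbidity scores 0 and all three groups can be filled; the documents give no data to estimate their sizes. The cost is a few lines of wording and a small change to the code list. No new data are needed.
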